## 9 CLINICAL PHARMACOLOGY PLAN

### 9.1 Pharmacology Objectives

- 9.1.1 To determine pharmacokinetic profile of single dose, subcutaneous VRC01 in HIV-1-exposed infants (Dose Groups 1 and 2).
- 9.1.2 To determine pharmacokinetic profile of monthly subcutaneous VRC01 in HIV-1-exposed infants (Dose Group 3).
- 9.1.3 To determine pharmacokinetic profile of one or two subcutaneous doses of VRC01LS (Dose Group 4)
- 9.1.4 To determine pharmacokinetic profile of one or two subcutaneous doses of VRC07-523LS (Dose Group 5)

### 9.2 Primary and Secondary Data

Demographic data (gender, ethnicity, weight, length, birth weight, gestational age at birth), dose group, VRC01, VRC01LS, or VRC07-523LS dose date, time, dose amount, administration location and sample collection times will be obtained. Plasma VRC01 (Dose Groups 1-3), VRC01LS (Dose Group 4), or VRC07-523LS (Dose Group 5) concentrations will be measured:

- Dose Groups 1 and 2: before dosing and on days 1, 3, 7, 14 and 28; then at Weeks 8, 16, 24, 48, and at HIV confirmation visits will be measured.
- Dose Group 3: before dosing (on days 0 and 28 and weeks 16, 20, 24); for breastfeeding, HIV-exposed uninfected infants after Week 24: 36, 48, 60, 72, and early D/C visit.); on days 1 and 14; and during the observation period: at the first visit after complete cessation of breastfeeding or HIV diagnosis, every 12 weeks thereafter and then at Weeks 84 and 96.
- Dose Group 4, Cohort 1: before dosing (Day 0) on Day 1, 14 and 28, and Week 8, 12, 24, 36, 48, 60, 72, 84 and 96. Cohort 2 infants will have these same visits and for those in Cohort 2 who receive a second VRC01LS dose at Week 12 due to continuing

to breastfeed, the Week 12 sample will be collected prior to their second dose and additional samples will be collected at Weeks 14 and 16.

- Dose Group 5, Cohort 1: before dosing (Day 0) on Day 1, 3, 7, 14 and 28, and Week 8, 12, 24, 36, 48, 60, 72, 84 and 96. Cohort 2 infants will have these same visits and for those in Cohort 2, infants who receive a second VRC07-523LS dose at Week 12 due to continuing to breastfeed, the Week 12 sample will be collected prior to their second dose and additional samples will be collected at Weeks 14 and 16.

Assay Site: Plasma pharmacokinetic samples collected will be sent per the study-specific Laboratory Processing Chart (LPC) and will be assayed for serum/plasma concentration of VRC01, VRC01LS, or VRC07-523LS.

Methods to be used: All assay methods will be standardized with a filed Methods Report, under Good Laboratory Practice (GLP) conditions. The assays will be performed using immune based method.

Reporting of Assay Data: At a minimum, assays will be conducted in batch after receipt of all samples through Week 8 for a particular participant in Dose Groups 1, 2, and 3 and through Week 12 for Dose Groups 4 and 5. Samples will be assayed within 60 days of the laboratory receiving the final Week 8 or Week 12 samples for Dose Groups 1-3 and 4-5, respectively. Samples received during the conduct of the study may be assayed prior to the final shipment. For Dose Group 5, Cohort 1, all samples collected to date will be assayed when the first six participants are enrolled. The designated lab will run the assays for VRC01, VRC01LS, and VRC07-523LS levels once per week as the trial begins and anti-drug antibody assays once per month. All PK samples will be registered in the Lab Data Management System (LDMS) database.

For the purposes of reporting initial PK results to clinicaltrials.gov, the  $AUC_{0-\tau_{\alpha}}$  and concentration at the end of the first dose interval,  $C_{\tau_{\alpha}}$ , time will be provided. For Dose Groups 1-3 these are  $C_{28D}$  and  $AUC_{0-28D}$  while for Dose Groups 4 and 5 they are  $C_{84D}$  and  $AUC_{0-84D}$ .

### 9.3 Study Design, Modeling and Data Analysis

Pharmacokinetic blood samples will be collected as noted in Section 9.2 and Schedule of Evaluation Appendices: APPENDIX IB: Infant Schedule of Evaluations (Dose Groups 1 and 2), APPENDIX ID: Schedule of Evaluations (Dose Group 3), APPENDIX IE: Schedule of Evaluations (Dose Group 4, Cohort 1: non-breastfeeding) APPENDIX IF: Schedule of Evaluations (Dose Group 4, Cohort 2: breastfeeding), APPENDIX IG: Schedule of Evaluations (Dose Group 5, Cohort 1: non-breastfeeding) and APPENDIX IH: Schedule of Evaluations (Dose Group 5, Cohort 2: breastfeeding). The samples will be 1-2 mL whole blood to yield 0.4-1.0 mL plasma. Sample volume will be dependent on infant weight (See APPENDIX IB: Infant Schedule of Evaluations (Dose Groups 1 and 2)).

VRC01, VRC01LS, and VRC07-523LS concentrations will be presented by study day, dose group and dose number. The frequency of achieving Day 28 concentrations greater

[figure not shown]
than 50  $\mu\text{g}/\text{mL}$  will be calculated. For Dose Group 4, the frequency of maintaining VRC01LS concentrations  $>50 \mu\text{g}/\text{mL}$  at Week 12 will be determined; likewise, for Dose Group 5, the frequency of maintaining VRC07-523LS concentrations  $>15 \mu\text{g}/\text{mL}$  at Week 12 will be determined. The median, mean and standard deviation of concentrations will be calculated from evaluable samples by each dose level. Evaluable samples are defined as samples with volume and integrity to generate accurate concentration results and their associated accurate dosing and sample times data. It is expected that VRC01 pharmacokinetic parameters will have similar variability as those seen in infants with RSV monoclonal antibodies by Meissner et al [50]; CV=34% for apparent clearance (CL/F) and CV=33% for apparent volume (Vd/F). With 10 completed participants planned from each dose group, it is expected that the 95% CIs for primary PK parameters for each dose group will be encompass a range of less than  $\pm 25\%$  of the point estimate values.

While it is expected that the CL/F for VRC01LS will be substantially lower than for VRC01, we expect the overall variability (CV) for PK parameters to be similar. Thus, the proposed study will generate a similar confidence interval in the VRC01LS pharmacokinetic parameters. Recent findings from VRC605 found the CV for VRC07-523LS AUC to be  $< 25\%$  for dosing groups receiving between 5-40 mg/kg and including following subcutaneous administration [62]. Based on these low variability values, the expected 95% CI will be tighter than those originally predicted for VRC01 based on RSV variability.

[figure not shown]
The observed VRC01, VRC01LS and VRC07-523LS concentrations will be compared to those seen in adults. Specifically, the geometric mean and 90% confidence interval for the Day 28 (VRC01) and Week 12 (VRC01LS and VRC07-523LS) concentrations will be generated. Based on RSV mAb pharmacokinetics in infants, it is expected that VRC01 Day 28 concentrations will fall within the range of 20-70  $\mu\text{g}/\text{mL}$  for the 20mg/kg dose (Dose Group 1) and 65-115  $\mu\text{g}/\text{mL}$  for the 40mg/kg dose (Dose Group 2). The predicted Week 12 VRC01LS and VRC07-523LS concentrations following 80-100mg SC are expected to be between 40-120  $\mu\text{g}/\text{mL}$  and 15-40  $\mu\text{g}/\text{mL}$ , respectively. These are lower than the predicted levels in adults at Week 12 in part due to a "diluting" effect from the large increase in body weight expected in the infants during the first 12 weeks of life. The predicted concentrations of VRC01 at 40 mg/kg and 20 mg/kg, VRC01LS at 20 mg/kg and VRC07-523LS at 80-100 mg are in Figure 7.

**Figure 7: Predicted VRC01, VRC01LS, and VRC07-523LS Concentrations**

[figure not shown]
VRC01 40MG/KG SINGLE DOSE MEDIAN (90% CI)

[figure not shown]
VRC01 20MG/KG SINGLE DOSE MEDIAN (90% CI)

VRC01LS 20MG/KG SINGLE DOSE MEDIAN (90% CI)

#### VRC07-523LS 80-100mg SINGLE DOSE MEDIAN (90% CI)

#### Individual Participant Pharmacokinetic Analysis

A non-compartmental pharmacokinetic analysis will be performed using WinNonlin or a similar program on the VRC01, VRC01LS, and VRC07-523LS concentration data generated from each participant in Groups 1, 2, 4, and 5. Calculated pharmacokinetic parameters will include: area-under-the-curve (AUC), maximum concentration ( $C_{max}$ ), time to  $C_{max}$  ( $T_{max}$ ), apparent clearance (CL/F), apparent volume of distribution (Vdz/F) and terminal elimination rate constant ( $\lambda_z$ ) and the terminal half-life.  $C_{max}$  and  $T_{max}$  will be taken directly from the observed concentration-time data. The terminal slope,  $\lambda_z$ , will be determined from log- linear portion of the curve and the half-life ( $T_{1/2}$ ) calculated as  $0.693/\lambda_z$ .  $AUC_{0-last}$  will be determined using the linear trapezoidal method. If the final samples have measurable VRC01, VRC01LS, or VRC07-523LS concentrations, the remaining AUC after the final concentration will be estimated as  $C_{last}/\lambda_z$ . For the purposes of determining Vdz/F, it will be calculated as the ratio of (CL/F) /  $\lambda_z$ . Data will be summarized based by each dose group and overall for CL/F, Vdz/F and  $T_{1/2}$ . The potential for non-linearity pharmacokinetics between Dose Groups 1 and 2 will be determined by comparing the dose-adjusted ratios for  $C_{max}$  and AUC between study dose groups. Additional compartmental analysis will be performed as warranted by the data from Dose Groups 1, 2, 4, and 5. For Dose Group 3, no intensive PK data is being collected; thus, the individual participant specific pharmacokinetic analysis will be limited to estimation of potential accumulation or decline in pre-dose concentrations with repeated dosing. For these calculations, the Day 28 pre-dose VRC01 concentration will serve as the reference with the pre-dose concentrations collected at later weeks divided by the Day 28 pre-dose VRC01 concentration. Both raw and dose adjusted (to 20mg/kg) concentration ratios will be calculated.

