For VRC01LS, the maximum serum concentrations in adults in VRC606 following IV administration of 20mg/kg and 40mg/kg were 1221±398 mcg/mL (n=8) and 2451±626 mcg/mL (n=3), respectively, with an overall half-life over 2 months. Following the single dose SC administration of VRC01LS 5 mg/kg, the  $C_{max}$  is reduced to levels about 25% of those seen following IV administration but the SC AUC is only reduced by about 20% compared to IV.

In preliminary PK studies of VRC07-523LS, adults who received 20 mg/kg (N=8) had a mean ( $\pm$  SD) day 28 concentration of 195 mcg/mL (+63) and a mean day 84 concentration of 37 mcg/mL (+5.5). While the levels at day 28 and 84 are lower than that seen with VRC01LS, due to the increased potency, it is expected that the ability of VRC07-523LS to neutralize virus will be similar or better than that of VRC01LS at these timepoints.

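### The linear trapezoidal rule over long late sampling gaps overstates full-curve AUC by about 4–7% for VRC01 and 4–5.5% for VRC07-523LS, so CL/F and Vdz/F come out low

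*Protocol*

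**What the plan says.** Protocol Section 9.3 plans a non-compartmental analysis of each infant in Groups 1, 2, 4 and 5, "using WinNonlin or a similar program". AUC0-last "will be determined using the linear trapezoidal method", with no separate rule for the declining part of the curve. If the last sample is measurable, "the remaining AUC after the final concentration will be estimated as" Clast/λz, and λz is taken from the log-linear part of the curve. CL/F follows from AUC, and Vdz/F is CL/F divided by λz.

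Section 9.2 gives the sampling times:

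- Dose Groups 1 and 2: "before dosing and on days 1, 3, 7, 14 and 28; then at Weeks 8, 16, 24, 48".
- Dose Group 5: "on Day 1, 3, 7, 14 and 28, and Week 8, 12, 24, 36, 48, 60, 72, 84 and 96".
- Dose Group 4: "before dosing (Day 0) on Day 1, 14 and 28, and Week 8, 12, 24, 36", then every 12 weeks.

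Section 9.2 also names the AUCs for the registry: AUC0-28D for Dose Groups 1–3 and AUC0-84D for Dose Groups 4 and 5. The SAP leaves all PK to a separate report and adds no integration rule.

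**The concern.** The plan treats the decline as exponential when it estimates λz and extrapolates the tail, but as a chain of straight lines when it integrates. For densely sampled curves this hardly matters. Here the late gaps span roughly one to five half-lives. A chord over a convex curve lies above it, so in the declining phase the error has one direction only. It does not average out over infants, and a larger sample would not remove it.

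The PK profile is a primary objective for every dose group, and AUC, CL/F and Vdz/F are among the planned parameters. All three inherit the error.

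**Working it through.** **The plan's own precision figure.** Section 9.3 expects 95% confidence intervals narrower than ±25% with 10 infants and CVs of 34% (CL/F) and 33% (Vd/F). The check is t(0.975, 9) × CV/√10 = 2.262 × 34%/3.162 = 24.3%, and 23.6% for 33%. The figure reproduces. The protocol gives no figure for integration error.

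**Inputs from the protocol**

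- VRC01 half-life in adults (Section 1.1.6): 15 and 12 days IV, 17 and 11 days SC. I carried the range to 20 days, the palivizumab value in infants in the same section.
- VRC07-523LS in adults (Section 1.1.6): 195 mcg/mL at Day 28 and "a mean day 84 concentration of 37 mcg/mL". The implied half-life is 56 × ln 2 / ln(195/37) = 23.4 days. The upper value of 40 days is my assumption.
- VRC01LS half-life in adults (Section 1.1.4): 71 ± 18 days.
- SC time to peak in adults (Section 1.1.6): 67 and 62 hours, about 2.7 days. I also used 5 days.

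**Error over one gap.** For a mono-exponential decline with x = gap × ln 2 / half-life,

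linear/true = (x/2)(1 + e^−x)/(1 − e^−x).

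| Antibody, half-life | Gap | x | Linear/true |
|---|---|---|---|
| VRC01, 15 d | 28 d | 1.294 | 1.14 |
| VRC01, 15 d | 56 d | 2.588 | 1.50 |
| VRC07-523LS, 23.4 d | 28 d | 0.831 | 1.06 |
| VRC07-523LS, 23.4 d | 84 d | 2.493 | 1.47 |
| VRC01LS, 71 d | 84 d | 0.820 | 1.055 |

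**Error over the whole curve.** Late gaps hold little of the area, so the single-gap figures must be weighted. I took noise-free profiles C(t) ∝ [ka/(ka − k)](e^−kt − e^−ka·t), with k = ln 2 / half-life and ka set by Tmax = ln(ka/k)/(ka − k). These were sampled at the Section 9.2 times down to 0.4% of peak (assumed). I integrated by each rule, added Clast/λz from the last three points, and compared with the exact area 1/k. With Tmax 2.7 days:

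| Segment | Share of true AUC0-inf | Linear error, points of total |
|---|---|---|
| VRC01, 15 d: Day 0–28 | 71.6% | +0.2 |
| Day 28–56 | 20.7% | +2.8 |
| Day 56–112 | 7.2% | +3.6 |
| Tail | 0.6% | 0 |
| **Total** | | **+6.6** |
| VRC07-523LS, 23.4 d: Day 0–28 | 55.6% | −0.2 |
| Day 28–84 | 36.0% | +2.05 |
| Day 84–168 | 7.7% | +3.65 |
| Tail | 0.7% | 0 |
| **Total** | | **+5.5** |

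CL/F is then 1/1.066 − 1 = −6.2% and 1/1.055 − 1 = −5.2%. Vdz/F moves by the same percentage, since λz is unaffected.

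**Range**

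| Quantity | Linear (planned) | Linear-up/log-down |
|---|---|---|
| VRC01 AUC0-inf, 11–20 d, limit 0.4% of peak | about +4 to +7% | −0.7 to −1.7% |
| VRC07-523LS AUC0-inf, 23.4–40 d, limit 0.4% of peak | about +4 to +5.5% | −0.4 to −0.7% |
| VRC01 AUC0-inf, limits 0.1–1% of peak | +2.9 to +7.4% | −0.7 to −1.7% |
| VRC07-523LS AUC0-inf, limits 0.1–1% of peak | +1.8 to +5.5% | −0.4 to −0.7% |
| VRC01 AUC0-28D (Dose Group 1–2 times) | −0.4 to +1.0% | −1.2 to −2.1% |
| VRC07-523LS AUC0-84D | +0.5 to +2.0% | −0.5 to −0.8% |
| VRC01LS AUC0-inf (Dose Group 4) | about 0 to +3% | −0.3 to −3.0% |

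Two-compartment profiles agree within about one point.

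**Against sampling error.** For VRC01, 6.2% ÷ (34%/√10 = 10.8%) = 0.58 SE. For VRC07-523LS, with the CV at its stated upper bound of 25% and 8 evaluable infants, 5.2% ÷ (25%/√8 = 8.8%) = 0.59 SE. A bias of this size lowers the coverage of a nominal 95% interval to about 91%.

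**The case against.** The linear rule is standard and openly stated, and little of importance depends on it. The PK targets in Section 9.3 are Day 28 and Week 12 concentrations, which need no integration. Dosing strategies come from population modelling and simulation, which do not use trapezoids. The only AUC comparison planned between groups is Dose Group 1 against 2. These share one schedule, so most of the error cancels in the ratio. (At a 15-day half-life the error is +6.6% if Week 16 is measurable and +3.0% if it is not, so a few points could remain if the two doses differ in their last measurable visit.) In Cohort 2 infants re-dosed at Week 12, the first dose interval has only 4-week late gaps and the error is about 2% or less. All of this stands, and it is why the point is minor.

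Three stronger readings are tempting, and the documents do not support them:

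- *Log-down integration costs nothing.* It does worse on the registry AUC0-28D for VRC01, where it is 1–2% low while the linear rule is within about 1%.
- *The comparison between antibodies is distorted.* The errors differ by only a few points, and no AUC or CL/F test between antibodies is planned.
- *Dose Group 4 needs its own correction because it has no samples between Day 1 and Day 14.* At the protocol's VRC01LS half-life the planned rule is only about 0–3% high on AUC0-inf, and log-down is up to 3% low. Taking that group from compartmental analysis would mix methods across groups.

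**Conclusion.** The concern holds as a small, systematic bias in full-curve AUC, CL/F and Vdz/F for Dose Groups 1, 2 and single-dose Dose Group 5. AUC0-inf is high by about 4–7% for VRC01 and 4–5.5% for VRC07-523LS, or about 2–7% across the quantification limits tried. It amounts to about 0.6 SE and lies well inside the planned ±25%. The PK targets, the population analysis and the registry AUCs are not materially affected.

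The direction was the same for these groups in every case run. The size rests on assumptions that the documents do not settle: infant half-lives like those of adults, no dilution by growth, noise-free profiles, and a last measurable level of 0.4% of peak (range 0.1–1%).

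**What to change.** In Protocol Section 9.3, Individual Participant Pharmacokinetic Analysis:

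- For full-curve AUC, CL/F and Vdz/F of the single-dose profiles in Dose Groups 1, 2 and 5, specify the linear-up/log-down trapezoidal method with actual sample times. Use the linear form where concentrations rise or a value is zero or unquantifiable.
- Keep the linear rule for the registry AUC0-28D. The check above covers the Dose Group 1 and 2 sampling times.
- For AUC0-84D in Dose Group 5, either rule is within about 2%. State which one is used.
- Leave Dose Group 4 as planned.

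The cost is one phrase in the protocol or PK analysis plan and one software setting. No new samples, visits or infants are needed, and the rule can be applied to data already collected. The downsides are that AUC will be slightly smaller and CL/F and Vdz/F slightly larger than under the planned rule, that a residual error of about 1–2% in the other direction remains, and that the PK report must label two integration rules.

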#### Interim Pharmacokinetic Analyses

Incremental pharmacokinetic analyses will be performed as data from Dose Groups 1-3 through Week 8 and through Week 12 for Dose Groups 4-5 becomes available. VRC01, VRC01LS and VRC07-523LS concentration data generated will be summarized and made available to the study team. Given the long half-lives of VRC01LS and to a lesser

degree VRC07-523LS, a more limited pharmacokinetic analysis will be performed on preliminary data. The focus of the Dose Groups 4 and 5 analyses will be on the Week 12 VRC01LS and VRC07-523LS concentrations. The purpose of these incremental analyses is to ensure that results are within the range of the expected targets. If these interim results demonstrate significant inter-patient variability, the team will determine if protocol modifications are required.

#### Population Pharmacokinetic Analysis

Population pharmacokinetic analyses will be performed on the VRC01 pharmacokinetic data from P1112 Dose Groups 1-3 to determine compartmental PK parameters with the program NONMEM. Based on VRC01 PK studies in adults and prior pharmacokinetic studies of antibodies in infants, a two-compartment model will be used to characterize the P1112 VRC01 PK data. Both zero and first order absorption model will be assessed to determine the structural pharmacokinetic model. Additional drug absorption models will be evaluated if dictated by the data. The population analysis will generate estimates for initial and final apparent volumes of distribution ( $V_1/F$  and  $V_2/F$ ), inter-compartmental clearance ( $Q/F$ ),  $CL/F$  and absorption rate parameters either  $KA$  or the zero-order rate constant ( $R_1$ ). Given the small participant numbers, the population pharmacokinetic analysis will not include an exploratory covariate analysis to assess clinical factors as fixed effects associated with VRC01 pharmacokinetic parameters with the exception of dose level (20mg/kg vs 40mg/kg) and repeat dosing as fixed effects on  $F$ ,  $KA/R_1$ ,  $CL$  and  $V_1/V_2$ .

[figure not shown]
This population analysis will be used to quantify the unexplained between participant pharmacokinetic variability. Final model selection will be based on changes in the objective function and graphically by goodness of fit plots. The final population model parameters will be assessed using bootstrapping to generate 95% CIs for parameter estimates and by visual posterior predictive check. Post-hoc empiric Bayesian estimates of individual participant's pharmacokinetic parameters will be generated. The population parameters and their variability will be used as the input model to assess different dosing strategies. Each VRC01 dosing strategy and its ability to achieve and maintain of target VRC01 concentrations will be performed using the final population pharmacokinetic model and Monte Carlo simulations with at least 5000 replicates.

Similar population PK analyses will be performed on the VRC01LS and VRC07-523LS concentration data from Dose Groups 4 and 5. These analyses will likely need to be nested with pharmacokinetic data from adults since the relatively sparse sampling and small number of P1112 participants receiving VRC01LS and VRC07-523LS will limit parameter estimate precision. Monte Carlo simulations will be used to predict the expected VRC01LS and VRC07-523LS concentrations with the study dose and distribution of Week 12 concentrations.

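### The VRC01 population PK model lists dose level and repeat dosing as its only covariate effects and states no body-weight term or parameter units, so, run as listed, the repeat-dosing term would absorb part of infant growth

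*Protocol*

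**What the plan says.** The population PK subsection of Protocol Section 9.3 pools VRC01 data from Dose Groups 1-3 in a two-compartment NONMEM model. It says: "Given the small participant numbers, the population pharmacokinetic analysis will not include an exploratory covariate analysis to assess clinical factors as fixed effects", and then makes two exceptions ("with the exception of dose level (20mg/kg vs 40mg/kg) and repeat dosing as fixed effects"), which may act on F, KA/R1, CL and V1/V2. The parameters are named without units, and no weight, allometric or age term is mentioned.

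Of the output it says: "The population parameters and their variability will be used as the input model to assess different dosing strategies". Section 9.4 expects the simulations to inform dosing in later infant trials.

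Elsewhere the protocol recognises growth. Section 9.3 attributes the lower Week 12 levels predicted in infants, relative to adults, partly to a diluting "effect from the large increase in body weight expected in the infants during the first 12 weeks of life". Section 9.2 lists weight among the PK data ("Demographic data (gender, ethnicity, weight, length, birth weight, gestational age at birth"), and Section 5.4 requires current weight on every prescription. Weight is given no stated role in the model.

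Section 9.3 plans similar models for VRC01LS and VRC07-523LS (Dose Groups 4-5), probably nested with adult data, and states no size scaling. SAP Sections 1.1 and 2.2 leave PK to a separate report by the study pharmacologist.

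**The concern.** Repeat VRC01 doses occur only in Dose Group 3, from Day 28 onward. In the pooled data, therefore, repeat dosing always goes with greater age and weight. If weight is absent, a repeat-dosing term is the natural place for the effect of growth to appear, and it can be mistaken for a real change in clearance or bioavailability with repeated doses.

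The data give limited help in separating the two. Dose Groups 1-2 have single-dose samples "before dosing and on days 1, 3, 7, 14 and 28; then at Weeks 8, 16, 24, 48", which in principle show growth without repeat dosing, but little antibody is left by the later visits. On the repeat-dose side, "For Dose Group 3, no intensive PK data is being collected", so the data say little about which parameter should carry the effect.

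What is at stake is narrow. A model can reproduce the visits it was fitted to and still mislead when it simulates ages or dosing intervals that were not studied, and simulation is its stated use.

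**Working it through.** **1. The plan's own precision figure.** Section 9.3 expects 95% intervals within ±25% with 10 infants per group, using "CV=34% for apparent clearance (CL/F) and CV=33% for apparent volume (Vd/F"). The half-width is t(0.975, 9) × CV/√n:
- CL/F: 2.262 × 0.34/√10 = 24.3%.
- Vd/F: 2.262 × 0.33/√10 = 23.6%.

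Both reproduce the figure. It describes sampling error around a correctly specified model and is silent on growth.

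**2. Why the direction depends on units.** Suppose V is proportional to weight.
- Absolute units: if weight is 1.5 times birth weight at a later dose (assumed), each mg enters a volume 1.5 times larger and gives 1/1.5 = 0.67 of the concentration. A constant-volume model reads this as lower F or higher CL after the first dose.
- Per-kg units: the dose is already divided by current weight, so that dilution cancels. What remains is growth between doses, which is fastest early. The base parameters absorb the rapid early dilution, and later doses are then diluted less than the model expects. It reads this as lower CL or higher F.

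**3. How much single-dose information remains late.** Protocol Section 1.1.6 gives adult SC half-lives of 17 and 11 days. Half-lives elapsed = days/half-life:
- Week 8: 56/17 = 3.3 to 56/11 = 5.1.
- Week 16: 112/17 = 6.6 to 112/11 = 10.2.

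**4. Refit with no true repeat-dose effect.** Concentrations were generated without noise for Dose Groups 1-3 on the protocol doses and sampling times, values below 1 µg/mL were dropped, and a constant-parameter one-compartment SC model was refitted by log least squares with one repeat-dose multiplier. The true multiplier is 1.00.
- Set A: 3.5 kg at birth (Protocol Section 3); half-life 11 or 17 days. Assumed: weight ×1.5 or ×2.0 by Week 12, V ∝ weight, CL ∝ weight^0.75 or weight^1, ka 0.4/day, 0.08 L/kg. Eight scenarios.
- Set B: half-life 15, 20 or 28 days. Assumed: three growth curves (birth 2.8/3.2/3.6 kg, Week 24 6.1/7.3/8.6 kg), CL and V ∝ weight, ka 0.5/day, 0.10 L/kg.

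| Model | Multiplier on | Set A | Set B |
|---|---|---|---|
| Absolute units, no weight | CL | 1.10-1.31 | 1.32-1.46 |
| Absolute units, no weight | F | 0.61-0.82 | 0.56-0.59 |
| Per-kg units, no weight | CL | 0.80-0.96 | 0.86-0.92 |
| Per-kg units, no weight | F | 1.08-1.51 | 1.17-1.25 |
| Current weight, correct exponents | CL or F | 1.00 | 1.00 |

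In Set B with zero growth every multiplier is 1.00, so growth is the cause. A false effect appears in every scenario, its sign reverses with the units, and in absolute units the two sets do not overlap. These ranges show the mechanism; none is an estimate for this trial.

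**5. Checks on the refit (Set A).**
- Without Dose Group 1-2 samples after Day 28, the ranges move little: absolute CL 1.09-1.29 and F 0.60-0.83; per-kg CL 0.75-0.96 and F 1.09-1.60. Late single-dose sampling therefore protects little, as step 3 suggests.
- RMS log misfit is at most 0.07 (0.04-0.09 in Set B), or up to 0.12 with Dose Group 3 samples to Week 72. The term thus takes up most but not all of the growth, and the misfit is small beside a 33-34% between-infant CV.
- Predicted Week 24 pre-dose level on the studied schedule: 0.90-1.15 of true.
- If weight enters with CL exponent 0.75 but the true exponent is 1, a false multiplier of 1.07-1.13 on CL, or 0.79-0.90 on F, remains.

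**The case against.** The protocol text is an outline. The quoted words are exceptions to a ban on exploratory searching, not a full model specification, and size scaling fixed in advance is a structural choice that the ban does not reach. The protocol clearly has growth in mind, and the PK work has its own report. A reader might infer that weight has been excluded. The documents do not say that; they are silent, and this part of the objection stands.

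The refit is also not the planned analysis. It has one compartment, no random effects and no noise, and it forces the repeat-dosing term in. The plan selects the final model by objective function and goodness-of-fit plots, then uses bootstrapping and a visual predictive check. With about 10 infants per group the term might not be retained, and no probability of retention was calculated. This stands too: the refit shows where growth goes if the term is kept, not how often that happens. It does not rescue the listed model, because the misfit left behind is small beside the expected variability, so the diagnostics may not reveal the cause.

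A reader might also carry the repeat-dosing argument over to the Week 12 targets in Dose Groups 4-5. The documents do not support that. The Week 12 sample is drawn before any second dose, so such a term is inactive there. The concern in those groups is different: size scaling is unstated when infant data are nested with adult data.

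**Conclusion.** The point holds as a gap in the stated model. As listed, the VRC01 model has no place for growth other than its base parameters, the repeat-dosing term and residual error, and the repeat-dosing term takes part of it. That conclusion rests on infants growing, which the protocol states, and on volume and clearance rising with weight, which is assumed.

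No size or sign should be quoted. The sign turns on units the documents do not give, and the size on assumed growth, half-life and scaling. It would be wrong to conclude that the trial's exposure results are biased: predictions on the studied schedule stay at about 0.90 to 1.15 of true, and the Day 28 and Week 12 target proportions, the non-compartmental analysis and the reported trough and AUC do not use this model. The exposure is confined to the population parameters and to simulations beyond the ages and intervals studied. This is a worthwhile, inexpensive improvement to the PK plan, not a defect in its main results.

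**What to change.** Add to the population PK plan, for all three products:
- Measured, time-varying body weight enters CL, Q, V1 and V2 a priori with pre-specified fixed exponents (for example 0.75 for clearances and 1 for volumes).
- Parameter units are stated as absolute or per kg, including where infant data are nested with adult data.
- A sensitivity analysis varies the exponents.
- Dose level and repeat dosing are evaluated only after weight is in, and the report says whether any repeat-dosing effect holds across the exponent runs.
- Simulations use age-appropriate weights.

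Keep the ban on exploratory covariate searching.

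The cost is a few sentences and a few lines of model code. Weight is already collected, and fixed exponents add no estimated parameter. The downside is that the exponents are assumed and do not capture maturation, so a wrong one leaves some residual false effect; the sensitivity run is there to expose it. If a separate PK plan already specifies this, a cross-reference is enough.
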